## **12.0 ADVERSE EVENT REPORTING**

**Considering the observational nature of this study, and lack of any experimental procedures, adverse event reporting will be limited only to those events that may occur from the specific non-standard of care lab procedures that are performed at 6 and 12 month visits. Adverse events at these 6 and 12 month visits are described here.**

### 11.1 Definitions

**Adverse events:** An adverse event is any undesirable clinical occurrence in a study patient, that is related to a study intervention that is non-standard of care. Any condition that was recorded as pre-existing or that is associated with standard of care procedures that the patient has consented to is not an AE unless there is a change in the nature, severity or degree of the condition.

**Serious Adverse Events (SAE):** Serious adverse events are defined by FDA regulation as any experience that results in a fatality or is life threatening; results in significant or persistent disability; requires or prolongs a hospitalization; or represents other significant hazards or potentially serious harm to research subjects or others, in the opinion of the investigators. Important medical events that may not result in death, be life-threatening, or require hospitalization may be considered a serious adverse event when, based upon appropriate medical judgment, they may jeopardize the patient and may require medical or surgical

intervention to prevent one of the outcomes listed in this definition. Examples of such medical events include bronchospasm requiring intensive treatment in an emergency room or at home, blood dyscrasias, or convulsions that do not result in inpatient hospitalization.

*Unanticipated Serious Adverse Event:* An unanticipated (unexpected) serious adverse event is any serious adverse event that is not protocol-defined or documented in the patient consent form. Expedited reporting is required for serious adverse events that are unexpected.

*Event Recording:* The following adverse events will be captured throughout the period of trial participation:

- Protocol-defined (as described below)
- Serious unanticipated events (serious “Other” adverse events)

*Causality:* The investigator will assess the relationship of an adverse event to the proposed non-standard of care lab assessments and imaging studies. Causality will be defined as follows:

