### *Reporting of Serious Adverse Events*

All investigators conducting the clinical study supported by the NHLBI must report both expected (protocol-defined) and unexpected serious adverse events. All serious adverse events must be reported as dictated by the specific IRB policy. Deaths unrelated to study participation will be reported to the IRB at the time of continuing review. Deaths related to study participation and associated with the non-standard of care procedures will be promptly reported to the IRB. The PI will notify the NHLBI program officer of any unexpected serious adverse events via e-mail within 24 hours of receipt of the event.

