### Wound Dehiscence

Disruption of the apposed surfaces of a surgical incision, excluding infectious etiology, and requiring surgical repair.

Other An event that causes clinically relevant changes in the patient's health, or any event that is life-threatening, results in a fatality, results in permanent disability, requires hospitalization, or prolongs an existing hospital stay.

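### A listed serious event counts as expected even when it is not a known reaction to the study-only test that caused it, so it misses the protocol's expedited rule and the 24-hour funder notice

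*Combined protocol and SAP*

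**What the plan says.** The opening of Section 12.0 states that "adverse event reporting will be limited only to those events that may occur from the specific non-standard of care lab procedures" at the 6- and 12-month visits. The definitions that follow (numbered 11.1, though they sit in Section 12.0) treat an event as adverse only if it is related to a study intervention outside standard care.

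The same subsection sets the test for expectedness: "An unanticipated (unexpected) serious adverse event is any serious adverse event that is not protocol-defined or documented in the patient consent form". It adds: "Expedited reporting is required for serious adverse events that are unexpected".

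Under Reporting of Serious Adverse Events, investigators "must report both expected (protocol-defined) and unexpected serious adverse events", which equates expected with protocol-defined. Three routes follow:

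- IRB, all serious events: "All serious adverse events must be reported as dictated by the specific IRB policy". No timeline is given.
- IRB, related deaths: "Deaths related to study participation and associated with the non-standard of care procedures will be promptly reported to the IRB".
- Funder: "The PI will notify the NHLBI program officer of any unexpected serious adverse events via e-mail within 24 hours of receipt of the event".

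The protocol-defined events are those under Specific Adverse Event Definitions. That list closes with an Other entry, which includes "any event that is life-threatening, results in a fatality, results in permanent disability, requires hospitalization, or prolongs an existing hospital stay".

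**The concern.** The section is meant to catch harm from tests that patients undergo only for research. By the Section 8.0 schedule these are blood draws and transthoracic echo at 6 and 12 months, and contrast MRI or transesophageal echo at 12 months; questionnaires and a walk test are also study-paid. For that purpose, expected should mean expected of the test. The rule instead asks whether the event type has an entry in a general list, and much of that list reads as if written for recovery from cardiac surgery, which the opening of Section 12.0 puts out of scope.

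The protocol's two fastest notification routes depend on this classification. If it is wrong, a serious and surprising harm of a research test can reach the funder and overseers later than intended, and a problem with a test could take longer to recognise.

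**Working it through.** No sample size, error rate or event count is involved. The check is to read the rules together and follow one event through them.

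**Does the list reach events that a late study test could cause?** The definitions fall into two groups.

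- *Tied to surgery:* the transfusion criterion for bleeding (counted from the operation), peri-CABG infarction, prolonged ventilation after surgery, and wound dehiscence. A test at 6 or 12 months can hardly meet these.
- *Time-neutral:* general myocardial infarction, stroke, arrhythmia with clinical compromise, major infection, renal events, and arterial and venous thromboembolism. These can be met at any visit, and their definitions do not refer to a study test.

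**Trace of one case: a non-fatal stroke judged related to the 12-month study imaging.**

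1. It is in scope: it is related to a study-only procedure at a 12-month visit (Section 12.0, opening; 11.1).
2. It is serious if it meets any seriousness criterion in 11.1, for example by needing hospitalization.
3. Stroke has its own entry under Neurologic Dysfunction, so the event is protocol-defined.
4. Under 11.1 it is therefore not unexpected, and the reporting paragraph labels it expected.
5. Expedited reporting covers unexpected events only, so it does not apply. The 24-hour NHLBI notice has the same trigger and does not apply either.
6. The prompt-report rule covers deaths, so it does not apply.
7. What remains is reporting under IRB policy, with no timing in the protocol.

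The same path holds for an infarction, or for an arrhythmia that meets the listed definition. If the event were fatal, step 6 would change and prompt IRB reporting would apply, but the 24-hour NHLBI notice would still not be triggered.

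**Comparison with the causality rules.** Probable and Possible both ask whether the event is a known reaction to the study-only procedure. Under Probable, an event that is not a known reaction can still qualify if nothing else reasonably explains it. So an investigator can conclude that a test probably caused a stroke and that stroke is not a known reaction to the test, and must still file it as expected.

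**Could the consent form change the result?** It was not available for this review. Under 11.1 it can only add to the expected events; it cannot make a listed event unexpected.

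**Exposure.** Planned enrolment is 125 + 15 = 140 patients, with two in-scope visits each: 140 × 2 = 280 visits at most. The true number will be lower, because Section 11.0 follows patients switched to valve replacement only at 12 months, and some patients will die or drop out. This counts visits, not events.

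**The case against.** **These events are still reported.** Correct. Every serious event goes to the IRB under its policy, which is not in the documents and may itself require prompt reporting. A reader might infer that such events escape reporting or are always reported late; the text does not support that. What is lost is the protocol's own expedited rule and the 24-hour NHLBI notice, and IRB policy does not replace a notice to the funder.

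**The whole list is surgical.** A reader might count the 13 named entries and conclude that every one is a perioperative complication that blocks expedited reporting. The documents do not support this. Many entries are time-neutral, and the truly surgical ones rarely block anything here. For instance, a serious non-fatal bleed after a study transesophageal echo that met none of the bleeding criteria would be unexpected unless the consent form names it, and would get the 24-hour notice. The problem lies in the time-neutral entries.

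**The Other entry makes every serious event protocol-defined.** Because Other closes the list and largely repeats the seriousness criteria, a reader might infer that no serious event can be unexpected, so that 0% of them are expedited. The Event Recording rule in 11.1 answers this: it separates protocol-defined events from serious unanticipated ones and identifies the latter as the serious Other events. The layout is untidy, but the unexpected class is not empty.

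**Some of these events are foreseeable.** In this population, infarction or stroke can occur as background illness, and the walk-test form lists angina-like symptoms and mental confusion as reasons to stop. That is fair, but foreseeing a symptom during a walk test does not make a stroke a known reaction to an MRI or a blood draw. The rule makes no such distinction.

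**The risk is small.** Section 1.0 rates the imaging risk as minimal. That limits how often the rule matters; it does not correct the classification when an event occurs.

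**Conclusion.** The point holds within limits. For a serious event that meets a time-neutral listed definition and is judged related to a study-only test, the protocol assigns the wrong class: expected by label, even when it is not a known reaction to the test. Such an event loses the expedited rule and the 24-hour NHLBI notice. IRB reporting remains, and so does prompt IRB reporting of related deaths.

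The size cannot be put as a number of events, because the documents give no event rate and none is assumed here. No endpoint or analysis is affected.

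The conclusion rests on two readings: that the 11.1 sentence means neither protocol-defined nor in the consent form, and that protocol-defined refers to the Specific Adverse Event Definitions. The reporting paragraph and the Event Recording rule support both. This is a wording defect worth correcting, because it falls on the events that the section exists to catch.

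**What to change.** Amend Section 12.0 in four places:

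1. In 11.1, replace the expectedness sentence with wording such as: *A serious adverse event is unexpected if its nature or severity is not a known reaction, as listed in the protocol or consent form, to the study-only procedure being assessed.* This uses the benchmark already in the causality rules.
2. State that the Specific Adverse Event Definitions are for coding only and do not make an event expected.
3. Under Reporting of Serious Adverse Events, remove the equation of expected with protocol-defined so that the paragraph matches 11.1.
4. Clarify at the Other entry that serious Other events belong to the unanticipated class, as the Event Recording rule says.

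If the consent form does not already list known reactions by procedure, a short list is needed there or in the protocol, since the new sentence depends on it. A reference to the timing in the IRB policy would also help.

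The cost is a short protocol amendment and possibly a few more expedited reports. Visits, tests and analyses do not change.

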**Probable**

Adverse events that, after careful medical evaluation, are considered with a high degree of certainty to be related to the proposed follow-up imaging and blood draw studies that are non standard of care.

The following characteristics will apply:

- A reasonable temporal relationship exists between the event and the procedure, and
- The event is a known reaction to the non-standard of care procedure, which can be explained by an alternative etiology commonly occurring in the population/individual, or
- The event is not a known reaction to the proposed non-standard of care procedure but cannot be reasonably explained by an alternative etiology.

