**Possible**

Adverse events that, after careful medical evaluation, do not meet the criteria for a probable relationship to the non-standard of care procedure, but for which a connection cannot be ruled out with certainty. The following characteristics will apply:

- The event occurs after non-standard of care procedure, and
- The event is not a known reaction to non-standard of care procedure, but cannot be explained by a commonly occurring alternative etiology

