### Unlikely

Adverse events that, after careful medical evaluation, do not meet the criteria for a possible or probable relationship to non-standard of care procedure for which a connection is unlikely. The following characteristics will apply:

- The event does not follow a reasonable temporal sequence from administration of the non-standard of care procedure, or
- May have been produced by environmental factors, and there is no apparent pattern of response to the non-standard of care procedure.

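### The Probable causality grade reverses its own test for a known reaction, and the 6- and 12-month limit on adverse event reporting fits neither the Section 8.0 schedule nor the surgery-tied event definitions

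*Combined protocol and SAP*

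**What the plan says.** All places are in the combined protocol and SAP.

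**Causality grades (Section 12.0, subsection 11.1 and the grade headings that follow).**
- Probable, lead sentence: the event is "considered with a high degree of certainty to be related to the proposed follow-up imaging and blood draw studies".
- Probable, second bullet: "The event is a known reaction to the non-standard of care procedure, which can be explained by an alternative etiology commonly occurring".
- Probable, third bullet: an event that is not a known reaction, "but cannot be reasonably explained by an alternative etiology".
- Possible, second bullet: "The event is not a known reaction to non-standard of care procedure, but cannot be explained by a commonly occurring alternative etiology". Its lead sentence reserves the grade for events that fail Probable.
- Unlikely is for events that fail both other grades and "for which a connection is unlikely". Its bullets name poor timing or environmental factors.

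**Scope.**
- Section 12.0 opens by limiting reporting to events that "may occur from the specific non-standard of care lab procedures that are performed at 6 and 12 month visits", and adds: "Adverse events at these 6 and 12 month visits are described here".
- Subsection 11.1 defines an adverse event as one "that is related to a study intervention that is non-standard of care", with no visit limit. Its Event Recording paragraph has protocol-defined events and serious unanticipated events captured for the whole of participation.
- The section on reporting serious adverse events requires expected and unexpected ones to be reported.
- Section 8.0 uses code 0 for study-paid items outside standard of care, and places that code at pre-op, discharge and 30 days as well as at 6 and 12 months.

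**The concern.** The second Probable bullet appears to have lost a *not*. As it stands, the presence of a competing explanation supports the highest causality grade, and its absence removes the case from the listed characteristics. Two investigators can therefore grade the same event differently, depending on whether they follow the lead sentence or the bullets. Relatedness has consequences in this protocol: a death that is related to participation and associated with the study procedures goes promptly to the IRB, while an unrelated death waits for continuing review.

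The scope wording raises a second problem. Staff cannot tell from Section 12.0 whether an event at an early study blood draw, or an event around surgery that meets one of the listed definitions, is to be recorded. No efficacy analysis uses these grades, so what is at stake is consistent safety recording.

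**Working it through.** The plan gives no figure to reproduce. The check is a reading of the grades case by case, followed by counts.

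**Step 1: grades from the bullets alone.** Take three yes/no features: reasonable timing, known reaction, common alternative cause. The event is assumed to follow the procedure, *reasonably* (Probable) and *commonly occurring* (Possible) are treated as the same test, and environmental factors are set aside. For a timely event:

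| Known reaction | Alternative cause | As written | With *cannot* in the second Probable bullet |
|---|---|---|---|
| yes | no | no grade | Probable |
| yes | yes | Probable | no grade |
| no | yes | no grade | no grade |
| no | no | Probable | Probable |

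- Row 1: Probable's second bullet needs an alternative, its third bullet and Possible's second bullet need a reaction that is not known, and Unlikely needs poor timing.
- Row 2: the bullets give Probable, which is hard to square with the certainty asked for in the lead sentence. Correcting the word moves this case to no grade, because Possible's second bullet admits only reactions that are not known.
- Row 3: no grade either way, unless the environmental-factors bullet of Unlikely is read to cover it.
- Row 4 also meets Possible's bullets, but Possible's lead sentence already ranks Probable first.

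So 2 of the 4 timely cases lack a grade as written, and 2 of 4 still lack one after the one-word change, though not the same two. For untimely events, three of the four cases are Unlikely. The fourth (not known, no alternative) is Possible if the timing bullet governs both other Probable bullets, and Probable if the third bullet stands alone after the *or*. The one-word change does not affect untimely events.

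**Step 2: study-paid procedures (Section 8.0, code 0).** There are 18 cells: pre-op 4, discharge 1, 30 days 1, 6 months 5, 12 months 7. Six are questionnaires (two each at pre-op, 6 and 12 months), so 18 − 6 = 12 are physical procedures, or 11 if only one of TEE and MRI is done at 12 months.
- Before the 6-month visit: pre-op 2 (walk test, blood) + discharge 1 (blood) + 30 days 1 (blood) = 4. As a share, 4/12 = 33% to 4/11 = 36%.
- This applies to Registry 1. Registry 2 has its first research point at 6 months, so none of the four arises there.
- Section 7.2 supports the three blood draws: the baseline laboratory assessment is marked as for study purposes only, and draws are listed at discharge and 30 days. The pre-op walk test rests on the Section 8.0 code alone.

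**Step 3: the scope sentences side by side.** The opening of Section 12.0 names lab procedures at two visits. The causality sentence in 11.1 names lab assessments and imaging. Probable's lead sentence names follow-up imaging and blood draws. None names the 6-minute walk test, although its form in Appendix 2 lists chest pain as a reason to terminate.

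**Step 4: event definitions.** The named types are bleeding, arrhythmia, pericardial fluid, hepatic dysfunction, infection, myocardial infarction, neurologic, renal, respiratory failure, right heart failure, arterial thromboembolism, venous thromboembolism and wound dehiscence: 13. Four contain a surgery-tied criterion: bleeding (transfusion within 24 hours of surgery), infarction (peri-CABG), respiratory failure (ventilation beyond 48 hours after surgery) and wound dehiscence (surgical incision). Two of the four set a fixed time, ending at day 1 and day 2. Section 7.2 allows ±30 days at 6 months, so that visit opens at 180 − 30 = day 150, or 183 − 30 = day 153, taking 6 months as 180 to 183 days. A criterion that closes by day 2 cannot describe an event arising from that visit.

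**The case against.** **The lead sentences govern.** A timely known reaction with no other cause plainly fits Probable's lead sentence, and most investigators would see the missing *not*. This stands. A reader might infer that the clearest related case cannot be graded at all, but the documents support that only when the bullets are read alone. What remains is that bullets and lead sentence point different ways. The second and third Probable bullets are joined by *or*, so they do not formally contradict each other; the test simply runs in opposite directions.

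**Probable and Possible do not compete.** Possible's lead sentence settles their overlap. This stands in full.

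**Adverse event is a defined term.** Read with its definition, the capture and reporting duties need not reach standard-of-care surgery. This is a fair reading, but it leaves the four surgery-tied definitions without a purpose. It does not rescue the 6- and 12-month limit either, since the definition covers study procedures at any visit and so includes the early blood draws.

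**The walk test is covered.** The adverse event definition does cover it, so a reader who infers that walk-test events fall outside the protocol goes too far. Only the causality sentence and Probable's lead sentence fail to name it.

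**Perioperative outcomes are collected anyway.** Section 9.0 includes mortality at discharge, stroke and valve re-intervention within MACE, and any-cause readmission in the first 30 days. The mismatch therefore does not mean that perioperative harm goes unseen. Nine of the 13 event types carry no surgery-tied criterion, and in bleeding, infarction and respiratory failure the surgical wording is one criterion or subtype among several.

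**Conclusion.** The concern holds as an error in the safety definitions that should be corrected. The second Probable bullet is reversed against its own lead sentence, so bullets and lead sentence disagree on timely known reactions. On the bullets alone, a timely event that is not a known reaction but has a common alternative also fits no grade, unless environmental factors are read to cover it. The reporting limit leaves out 4 of 11 to 12 physical study-paid procedures in a Registry 1 patient, and 4 of 13 event types contain criteria that fit neither that limit nor the adverse event definition.

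The size is modest. The early procedures are three blood draws and one walk test. A reader might infer damage to the trial's results, but nothing in the documents ties these grades to sample size, power or the primary analysis. The conclusion rests on the simplifications in Step 1 and on the Section 8.0 codes as printed; without the pre-op walk test, the early procedures number 3 of 10 to 11.

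**What to change.** 1. In the second Probable bullet, change *can be explained* to *cannot be explained*.
2. Reconcile Probable, Possible and Unlikely together, so that every combination of timing, known reaction and alternative cause has exactly one grade. The word change alone is not enough: a timely known reaction with a common alternative, and a timely event that is not a known reaction and has one, must each be placed.
3. In the opening of Section 12.0, the causality sentence of 11.1 and Probable's lead sentence, use one scope wording that covers every procedure coded 0 in Section 8.0, including the walk test.
4. Reconcile the opening of Section 12.0 and the definitions in 11.1 with the serious adverse event reporting duty and the specific event definitions, and state whether perioperative events are recorded. That scope is for the sponsor and the IRB to choose.

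Cost: one wording amendment, with no new visit, test or patient. Chart-based data entry is added only if the sponsor and the IRB decide to record perioperative events.
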